5.1.2 Previous and Concomitant Treatment (Medication and Nonmedication Therapy)

Systemic antifungal medications taken for IM or IA or suspected mycoses and other medication taken within 28 days prior to the screening visit and up to the first dose of study

drug (investigational period) will be documented as prior antimycotic medications or other prior medication, respectively.

Medications taken after the first dose of study drug and up to EOS will be documented as concomitant medications.

Prior and concomitant medications and nonmedications to be documented include, but are not limited to, the following: vitamins, herbal remedies (e.g., St. John's Wort, valerian) and over-the-counter and prescription medications. Any medications taken for treatment of pain symptoms will be documented as such.

Subjects are instructed not to take any concomitant medication without first consulting the investigator or study coordinator throughout the duration of the study.

Prohibited Therapies:

Treatments with concomitant drugs that are strong inhibitors or inducers of CYP3A4 are prohibited, including ketoconazole, high dose ritonavir, rifampin/rifampicin, carbamazepine and St. John's Wort or long acting barbiturates (e.g., phenytoin). Concomitant use of sirolimus, atorvastatin, cyclosporine, tacrolimus, midazolam, bupropion, mycophenolate mofetil and digoxin should be made with caution.

Treatments with concurrent drugs that are CYP3A4 substrates and have a narrow therapeutic range (e.g., vincristine) should be used with caution, and if clinically warranted, consider reduction of substrate dose.

Use of other systemic antifungals is prohibited during study drug administration.

Subjects taking prohibited medications who are willing to discontinue these medications, as clinically indicated and based upon the investigator's recommendation, may washout over a period of 5 half-lives on a schedule determined by the investigator.

5.1.3 Treatment Compliance

Study drug is administered at the research facility under the supervision of study personnel while the subject remains as an inpatient.

If the subject is discharged while continuing treatment with intravenous dosing, the subject must return to the research facility or other approved location every day to receive the daily intravenous dose. Vital signs will be taken pre and post dose. Infusion reaction and other safety monitoring will be conducted.

Subjects who are discharged from the hospital with oral capsules for at-home administration must return weekly for study drug accountability and to receive new oral dosing supplies. Subjects will be provided with approximately 1-week worth of study medication, dosing instructions and a daily dosing log for documentation of ingestion of the oral study medication.

The subject or parent/legal guardian must record the date and time of oral dosing once the first capsule is ingested. The subject should ingest the entire dose within 5 minutes. If the entire dose is not ingested within 5 minutes, record the reason for dosing delay in the source

documentation. If the subject should vomit any of the medication, this is to be recorded as well. The dose is NOT to be repeated. Compliance of the study drug will be monitored by review of the oral dosing log and the accounting of unused medication returned by the subject at each scheduled visit after day 7 and/or at the EOT visit.

When study drug is administered at the research facility, it will be administered under the supervision of study personnel. A subject daily dosing log will be collected to record date/time and completeness of dosing for each day.

Study subjects and their parents/legal guardians should be counseled on the need to meet 100% compliance with study drug dosing. The investigator or designee should ensure that study subjects adhere to this goal throughout the study.

If compliance is less than 80%, the investigator or designee is to counsel the subject and ensure steps are taken to improve compliance.

5.2 Demographics and Baseline Characteristics

5.2.1 Demographics

Demographic characteristics will be recorded at the screening visit. This will include age, sex, race, ethnicity (if known), height and body weight. Height and weight are to be measured while the subject is clothed, but not wearing shoes.

5.2.2 Medical History

The medical history of diseases other than the underlying diseases or conditions or infectious diseases will be identified at screening, by means of diagnosis and duration of the disease.

The medical history will include information related to the duration (i.e., the number of months or years). Subject's relevant medical and surgical history must be documented.

5.2.2.1 Underlying Diseases or Conditions

At screening, all underlying diseases or other conditions that predispose the subject to IFIs will be recorded.

5.2.2.2 Infectious Disease History

History of all fungal, viral and bacterial infections within 14 days prior to screening will be recorded.

5.3 Efficacy and Pharmacokinetic Assessments

5.3.1 Efficacy Assessment

All clinical, mycological, radiological assessments and diagnostic tests performed to document the baseline mould infection must be recorded. Criteria for possible, probable and proven disease based on the EORTC/MSG criteria require evidence including host factors (neutropenia, hematological malignancy, etc.), mycological criteria (positive culture from normally sterile site, BAL fluid, serum or BAL GM and histology of tissue demonstrating the

presence of fungal elements), and clinical signs and symptoms (radiological evidence of fungal disease at the infected body site). These data will be recorded in the eCRF.

During treatment with study drug, record any tests performed to demonstrate changes from baseline or evaluate the status of the fungal infection, such as mycological evidence of fungal culture or histology results (positive and negative) from the relevant site of infection or any new site, new fungal infection, changes in clinical signs and symptoms, including radiological findings relevant to the baseline fungal infection under treatment, and any serological markers performed (serum GM) and any surgical procedures. Record any procedures conducted to further assess or treat the fungal infection such as surgical debridement, amputation, etc. and the results of such procedures. Negative results of tests demonstrating resolution of infection should also be documented and recorded in the eCRF. Mortality status will be assessed per [Table 1 and Table 2 Schedule of Assessments].

Every effort should be made to speciate and characterize any fungal organisms grown in cultures. Results of susceptibility testing done locally will be collected. Fungal isolates from all positive fungal cultures should be stored and a reference laboratory will be made available by the sponsor. The reference laboratory will provide confirmation of the fungal genus and species, as well as in vitro susceptibility to isavuconazole, as well as relevant mould-active antifungal drugs. The reference laboratory results will not be available until after the end of the study.

5.3.2 Pharmacokinetic Assessment

Blood samples will be collected for pharmacokinetic analysis of isavuconazole as depicted in [Table 1 and Table 2 Schedule of Assessments]. Blood sample collection, handling and storage will be described in the laboratory manual.

Blood sampling for the analysis of trough levels will be obtained from all subjects. The samples should ideally be drawn immediately prior to the dose of study drug, but must be taken no earlier than 1 hour prior to the dose on days 7, 14, 21, 42 and 84 or EOT.

In addition to the above, 24-hour pharmacokinetic samples for intravenous or oral dosing will be obtained on any one day between day 14 and day 42, while the subject is still receiving study drug, for subjects who consent to participation in the 24-hour pharmacokinetic assessment. The goal is to achieve approximately 6 subjects in each age cohort by the time enrollment is completed for the study.

The 24-hour **intravenous** pharmacokinetic samples will be obtained as follows:

1. within 1 hour prior to the start of the intravenous isavuconazonium sulfate infusion (this sample will be the same as the trough sample prior to dose if it coincides with scheduled days 14, 21 or 42);
2. immediately after the completion of the intravenous infusion (no more than 5 minutes after);
3. within 4 to 10 hours after the start of the intravenous infusion; and
4. within 16 to 24 hours after the start of the intravenous infusion (must be obtained before the start of the next infusion).

The 24-hour **oral** pharmacokinetic samples will be obtained as follows:

1. within 1 hour of next oral dose (this sample will be the same as the trough sample prior to dose, if it coincides with scheduled days 14, 21 or 42);
2. 1 hour post dose (\pm 10 minutes);
3. 3 hours post dose (\pm 10 minutes);
4. 4 hours post dose (\pm 10 minutes);
5. within 6 to 8 hours (\pm 30 minutes) of study drug administration; and
6. 24 hours (within 1 hour before next study drug administration) after study drug administration.

5.3.3 Oral Dosing Acceptability Assessment

This assessment will be conducted to assess the acceptability of the new oral formulation in this subject population. Subjects who begin oral administration of the study drug will complete an assessment shortly after taking their first oral dose. A 5-point hedonic scale rating the oral dosing is included on the assessment. There are 5 faces with descriptions from really bad to really good that rank the response to the following questions:

- How was the TASTE of the medication?
- How was it to SWALLOW the medication?
- How would you FEEL if you took this medication again?

Refer to [Appendix 12.7 Oral Dosing Acceptability Assessment].

5.4 Safety Assessment

5.4.1 Vital Signs

Vital signs (temperature, pulse rate and blood pressure) are to be measured within 1 hour before the start and approximately 1 hour after the end of each infusion on dosing days. No additional vital signs are needed on dosing days for oral administration. Temperature to be taken as per institution's policy based on age of subject. Vital signs will be collected as shown in the schedule of assessments [Table 1 and Table 2]. When vital signs are scheduled for the same time as a blood sample, the vital signs will be taken before the blood sample.

5.4.2 Laboratory Assessments

Below is a table of the laboratory tests that will be performed during the conduct of the study and assessed by the local laboratory. In the event the protocol-specified clinical laboratory has already been collected and results available, these data are sufficient for monitoring safety as per the protocol and must be recorded in the eCRF. In order to minimize blood draws, it is not necessary to draw an additional sample for the sole purposes of the clinical trial.

Clinical laboratory samples should be collected at the same time as other blood samples such as pharmacokinetic whenever possible to minimize the need for unnecessary blood sampling for the subject. See [Table 1 and Table 2 Schedule of Assessment] for study visit days and allowed windows for lab sample collection.

Chemistry:	Hematology:
Sodium	Red blood cells
Potassium	White blood cells (total leukocytes)
Magnesium	Hemoglobin
Calcium	Hematocrit
Chloride	Platelets (thrombocytes)
Glucose	Neutrophils (ANC)
Creatinine	Eosinophils
Creatine phosphokinase/Creatine kinase	Basophils
Alkaline phosphatase (ALP)	Lymphocytes
	Monocytes
	Blast cells
Hepatic Panel:	Pregnancy Test:
Albumin	Human chorionic gonadotropin (hCG)
Total bilirubin (TBL)	
Direct Bilirubin	
Total Protein	Other:
Alanine aminotransferase (ALT)	Serum galactomannan (GM)
Aspartate aminotransferase (AST)	Partial thromboplastin time/international normalized ratio (PTT/INR)

Clinically significant out-of-range laboratory findings are to be determined and documented by the investigator/subinvestigator who is a qualified physician. Clinically significant changes will be recorded as AEs. At all scheduled time points during the clinical study, should any of the clinical laboratory test results be outside the normal range, the investigator may decide to repeat tests on new samples. A urine or serum pregnancy test will be performed for female subjects of childbearing potential prior to dosing, day 28, day 42 and day 84 (IA) or EOT, day 180 (IM) or EOT.

5.4.3 Physical Examination

Subjects will be examined by a medically qualified person at the times specified in [Table 1 and Table 2 Schedule of Assessments].

A complete physical examination consisting of an examination of general appearance, eyes, nose, throat, neck (including thyroid), lymph nodes, chest, lungs, cardiovascular, abdomen, skin, extremities, musculoskeletal and neurological system including mental status is to be conducted. A symptom-directed physical exam may be performed during subsequent visits, if necessary.

Height will be measured at screening only. Weight will be measured at screening, day 84 or EOT (IA and IM subjects) and/or day 180/EOT (IM subjects).

The screening physical examination also includes significant, ongoing medical conditions. Any changes between screening and day 1 are to be captured in the medical history.

Any abnormal finding(s) at screening must not be exclusionary per the eligibility criteria if a subject is to be enrolled in the study. Post initial study drug dosing, new abnormal findings or a worsening of an ongoing abnormal condition must be recorded as an AE.

5.4.4 Electrocardiogram

Standard 12-lead ECG recordings will be used for the purposes of safety assessment by the investigator.

A 12-lead, resting ECG is to be recorded, as indicated in [Table 1 and Table 2 Schedule of Assessments]. Subjects should remain supine for at least 5 minutes prior to all ECGs being performed. Dates and times may be generated by the machine's internal clock and are considered source data. The results are to be interpreted by qualified personnel in real time. The principal investigator/ designee will initial and date and provide his/her clinical interpretation on each report. The results (normal, abnormal not clinically significant, abnormal clinically significant) are to be recorded.

The ECG recorded during screening will be used to determine eligibility for study participation. Subjects who have familial short QT syndrome, or a clinically significant abnormal ECG, will not be eligible for the study. The interpretation of the ECG from screening will be the baseline to which post study drug dosing ECGs will be compared.

ECGs will be performed at screening and prior to study drug administration on each scheduled day as indicated in [Table 1 and Table 2 Schedule of Assessments].

Unscheduled ECGs will be performed if clinically indicated.

The original printout and an electronic copy of all scheduled and unscheduled ECG tracings should be maintained on site as source data.

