1.2 Nonclinical and Clinical Data

An overview of the nonclinical and adult clinical data of isavuconazole can be found in the latest version of the investigator's brochure (IB).

Isavuconazole has been investigated in a phase 1 pharmacokinetic, safety and tolerability study in pediatric subjects following intravenous administration. In this study, a total of 27 pediatric subjects received at least 1 dose of study drug (Protocol 9766-CL-0046). Nine subjects were between 1 and < 6 years of age, 8 subjects were between 6 and < 12 years of age and 10 subjects were between 12 and < 18 years of age. A majority of subjects were white and male. Most subjects had an underlying malignancy. Subjects weighing \leq 40 kg received 10 mg/kg of isavuconazonium sulfate, and subjects > 40 kg received 372 of isavuconazonium sulfate intravenously daily, after a loading regimen.

The vast majority of subjects experienced at least 1 adverse event (AE), and serious adverse events (SAEs) were experienced by about half of all subjects, which is expected given the medical history of the subjects enrolled. About a third of subjects experienced drug-related AEs. Important drug-related events included gastrointestinal (GI) disorders and infusion-related reactions. Two subjects were withdrawn from the study due to an AE. The events leading to withdrawal were increased liver enzymes and QT prolongation, and both events were considered related to study drug. No differences were observed in the AE experience between the 3 age cohorts.

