3.3 Exclusion Criteria

Subject will be excluded from participation if any of the following apply:

1. Subject has familial short QT syndrome, is receiving medications that are known to shorten the QT interval, or has a clinically significant abnormal ECG.
2. Subject has evidence of hepatic dysfunction defined as any of the following:
 - Total bilirubin (TBL) ≥ 3 times the upper limit of normal (ULN)
 - Alanine transaminase (ALT) or aspartate transaminase (AST) ≥ 5 times the ULN
 - Known cirrhosis or chronic hepatic failure

3. Subject has used strong cytochrome P450 (CYP3A4) inhibitors or inducers such as ketoconazole, high dose ritonavir, rifampin/rifampicin, long acting barbiturates (e.g., phenytoin), carbamazepine and St. John's Wort in the 5 days prior to the first dose of study drug.
4. Subject has another IFI other than possible, probable or proven IA or IM.
5. Subject has chronic aspergillosis, aspergilloma or allergic bronchopulmonary aspergillosis.
6. Subject has received mould active systemic antifungal therapy, effective against the primary IMI, for more than 4 days during the 7 days preceding the first dose.

Note: Prior use of prophylactic antifungal therapy is acceptable. In case of breakthrough IA while on prophylactic mould-active azole class drugs, additional documentation will be required to be submitted to the sponsor medical monitor or designee to approve subject enrollment.

7. Subject has known history of allergy, hypersensitivity or any serious reaction to any of the azole class antifungals, or any components of the study drug formulation.
8. Subject has any condition, which, in the investigator's opinion, makes the subject unsuitable for study participation.
9. Subject is unlikely to survive 30 days in the investigator's opinion.
10. Subject has received investigational drug, with the exception of oncology drug trials, or trials with investigational drugs treating graft versus host disease, within 28 days or 5 half-lives, whichever is longer, prior to screening.

Waivers to the exclusion criteria will **NOT** be allowed.

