7.5.5 Routine 12-lead Electrocardiograms

All 12-lead ECG results will be summarized by time point.

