| ICH | International Conference on Harmonization |
| IFD | Invasive Fungal Disease |
| IM | Invasive Mucormycosis |
| INR | International normalized ratio |
| IV | Intravenous |
| K-M | Kaplan-Meier |
| LLOQ | Lower Limit of Quantification |
| MedDRA | Medical Dictionary for Regulatory Activities |
| N | Sample Size |
| PD | Protocol Deviation |
| PK | Pharmacokinetic |
| PKAS | Pharmacokinetics Analysis Set |
| PPK | Population Pharmacokinetics |
| PT | Preferred Term |
| PTT | Partial thromboplastin time |
| QTc | Corrected Q-T Interval |
| SAE | Serious Adverse Event |
| SAF | Safety Analysis Set |
| SAP | Statistical Analysis Plan |
| SAS | Statistical Analysis Software |
| SD | Standard Deviation |

| Abbreviations | Description of abbreviations |
|----------------------|-------------------------------------|
| AC | Adjudication Committee |
| SOC | System Organ Class |
| TBL | Total bilirubin |
| TEAE | Treatment Emergent Adverse Event |
| TLF | Tables, Listings and Figures |
| ULN | Upper Limit of Normal |
| US | United States |
| WHO | World Health Organization |

List of Key Terms

| Terms | Definition of terms |
|------------------------|--|
| Adverse Event | An adverse event (AE) is any untoward medical occurrence in a subject or clinical investigation subject who has been administered a pharmaceutical product (remark: this means any investigational medicinal product) and which does not necessarily have a causal relationship with this treatment. An AE can therefore be any unfavorable and unintended sign (including an abnormal laboratory finding), symptom, or disease temporally associated with the use of a medicinal product, whether or not related to the medicinal product. |
| Baseline | Baseline is the time point prior to the first dose of study medication. The last measurements/evaluation prior to first dose of therapy is considered the baseline measure/evaluation. |
| Investigational period | Period of time where major interests of protocol objectives are observed, and where the test drug is usually given to a subject, and continues until the last assessment after completing administration of the test drug as stated in the protocol regarding V5 (End of Trial). |
| Screening | Process for retrieving candidates for the study. Process for checking the eligibility of subjects usually done during the “pre-investigational period”. Screening evaluations will be performed on the same day of study enrollment. |

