6.5.5 Routine 12-lead Electrocardiograms

Number and percent of subjects with 12 lead ECG abnormalities as well as number and percent of subjects whose 12 lead ECG reading changed from normal at baseline to abnormal will be tabulated by Analysis Visit.

The number and percentage of subjects who have treatment emergent changes toward worst category in the ECG interpretations assessed by investigators will be calculated. The interpretations are the followings: Normal, Abnormal-clinically relevant and Abnormal-not clinically relevant. Subjects who have both baseline and at least one post-baseline value will be included.

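### ECGs are recorded and analysed only as a three-level investigator reading, so a QTc shift that is not judged clinically significant appears in no planned table; the two documents can also select different ECG baselines.

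*Protocol*

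**What the plan says.** ECG is a named safety endpoint in both documents (protocol 2.3.1, SAP 5.1), and safety is the first listed objective.

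- **Recorded.** Protocol 5.4.4: "The results (normal, abnormal not clinically significant, abnormal clinically significant) are to be recorded". Printouts and electronic copies of the tracings stay at the site.
- **Analysed.** Protocol 7.5.5: "All 12-lead ECG results will be summarized by time point". SAP 6.5.5 plans "Number and percent of subjects with 12 lead ECG abnormalities as well as number and percent of subjects whose 12 lead ECG reading changed"; the change meant is a move out of the normal category after baseline. It also plans shifts toward the worst category. On the categories it says: "The interpretations are the followings: Normal, Abnormal-clinically relevant and Abnormal-not clinically relevant". QTc is in the SAP abbreviation list and nowhere else in the SAP.
- **QT as a concern.** Exclusion criterion 1 (protocol 3.3) begins: "Subject has familial short QT syndrome, is receiving medications that are known to shorten the QT interval". On the previous pediatric study, protocol 1.2 reports: "The events leading to withdrawal were increased liver enzymes and QT prolongation, and both events were considered related to study drug".
- **Baseline.** Protocol 5.4.4: "The interpretation of the ECG from screening will be the baseline to which post study drug dosing ECGs will be compared". SAP List of Key Terms, under Baseline: "The last measurements/evaluation prior to first dose of therapy is considered the baseline measure/evaluation". SAP 6.5.5 gives no ECG baseline of its own.

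**The concern.** The exclusion criterion points to QT shortening and the previous pediatric study to prolongation. A category of normal or abnormal shows neither direction nor size, and in the ECG tables it does not separate a QT finding from any other abnormality. If QTc moved by a modest amount in most children, the planned ECG tables could look unremarkable, and a reader of the study report could not tell a small effect from none. The information would exist on the tracings but not in the database.

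The baseline wording raises a second, smaller problem: the count of children who go from normal to abnormal depends on which pre-dose ECG is called baseline.

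**Working it through.** The documents state no ECG figure to reproduce. The check compares the text with the schedule and adds illustrations under stated assumptions.

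**1. What is already collected.** Table 1 marks ECGs at screening and Days 1, 7, 14, 28, 56 and 84/EOT: 7 per child, so 7 × 30 = 210 tracings at most. Table 2 adds up to 4 for mucormycosis subjects (Days 85, 115, 145, 180). Troughs are on Days 7, 14, 21, 42 and 84/EOT. The shared days are 7, 14 and 84/EOT, so at most 3 × 30 = 90 ECG–trough pairs. Footnote 6 to Table 1 and footnote 4 to Table 2 put every scheduled ECG before that day's dose.

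**2. What the adverse-event route can show.** Protocol 1.2 reports two withdrawals among 27 children, taken here as one for each named event.
- QT withdrawal rate: 1/27 = 3.7% (exact 95% CI 0.1% to 19.0%).
- Chance of at least one such event at that rate: 1 − (26/27)^30 = 68% with 30 children; 1 − (26/27)^25 = 61% with 25.
- Upper exact 95% limit if none is seen: 1 − 0.025^(1/30) = 11.6% with 30; 13.7% with 25.

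**3. What numeric QTc would show.** Half-width of the 95% CI for a mean change = t(0.975, n−1) × SD/√n. The documents give no SD, so a range is assumed.

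| Assumed SD of change (ms) | n = 30 | n = 25 |
|---|---|---|
| 10 | 3.7 | 4.1 |
| 15 | 5.6 | 6.2 |
| 20 | 7.5 | 8.3 |
| 25 | 9.3 | 10.3 |

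**4. How a category handles a modest shift.** Simulation, all inputs assumed: baseline QTc with SD 20 ms, change with SD 15 ms, and a reading called abnormal only at 450 ms or above or at 350 ms or below. Expected number going from normal to abnormal at one visit, per 30 children normal at baseline:

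| Mean shift (ms) | Baseline mean 400 | 410 | 420 |
|---|---|---|---|
| −10 | 1.7 | 1.1 | 1.0 |
| 0 | 1.1 | 1.4 | 2.3 |
| +10 | 1.7 | 3.0 | 5.0 |

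Under these assumptions a shift of 10 ms moves the count by about 0.3 to 2.7 children, and a shortening can lower it.

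**5. Baseline.** Table 1 marks a screening ECG (Day −5 to Day 1 predose) and a Day 1 ECG, also predose. A clinically significant abnormal ECG is exclusionary, so an enrolled child's pre-dose readings should be normal or abnormal not clinically significant.
- Both readings the same: the two rules agree.
- Screening normal, Day 1 abnormal: a later abnormal reading counts as a change under the protocol rule, not under the SAP rule.
- Screening abnormal, Day 1 normal: the reverse.

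**The case against.** The strongest reply is that clinically significant QT findings are not lost. Protocol 5.5.1.1 has clinically significant ECG abnormalities not related to underlying disease reported as adverse events; these are coded and tabulated by preferred term (protocol 7.5.1, SAP 6.5.1). That stands, and for those events the cause is visible. It does not reach readings judged normal or not clinically significant, or those attributed to underlying disease and no more severe than expected.

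Other points that stand:
- There is no QT objective and the trial is descriptive. Protocol 1.4 singles out liver toxicity for close monitoring, and the program includes a thorough QT study in adults (protocol 2.2.2).
- Stored tracings could be re-read. The eCRF and the table specifications are not among the documents, so the point rests on what protocol and SAP say is recorded.
- An uncontrolled QTc change cannot be attributed to the drug, local readings are noisy, and pre-dose ECGs miss peak exposure.
- 210 tracings and 90 pairs are ceilings. Treatment stops at a successful outcome, protocol 1.1 cites 30% and 31% mortality at 12 weeks, and an early EOT sample may not be a pre-dose trough.
- The SAP baseline is a general key term. The protocol's screening period runs until just before dosing, and SAP Appendix 1 uses one screening-and-baseline window, so both rules can select the same ECG.

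A reader might infer that the trial cannot detect any QT effect, or would report an absence of ECG signal without having looked. The adverse-event route and the retained tracings do not support that.

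**Conclusion.** The gap is real but limited. As specified, no planned table would show a QTc shift read as normal or not clinically significant, or its direction and size; clinically significant QT events can still appear as adverse events. Numeric capture would give a mean change to within about 4 to 9 ms with 30 children, or 4 to 10 ms with 25, if the SD of change is 10 to 25 ms. That is precision for a within-group change, not evidence of a drug effect, and it falls as children leave treatment. This is a cheap improvement, not a flaw that undermines the safety analysis.

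The baseline difference is a separate, minor inconsistency. It is tempting to read it as affecting all the ECG results; it alters the normal-to-abnormal counts only for children whose screening and Day 1 pre-dose readings differ. How many that would be cannot be known from the documents.

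**What to change.** - **Protocol 5.4.4 and eCRF.** Enter heart rate and QT from each tracing already taken. Derive QTc centrally with one named correction formula, because sites may use different ones.
- **SAP 6.5.5.** Name the formula. Summarise QTc change from baseline by visit, and list each subject's largest increase and largest decrease. Optionally, plot the change against the same-day trough for Days 7, 14 and 84/EOT, giving the number of pairs actually available.
- **Limits to state with the tables.** Local readings are noisy; there is no control arm; all scheduled on-treatment ECGs are pre-dose, so effects at peak exposure are not measured.
- **Baseline, both documents.** Use the last pre-dose ECG. Eligibility can still rest on the screening ECG. The choice matters more once QTc is numeric, since two pre-dose tracings will rarely give the same value.

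Cost: two numeric fields per ECG, at most 2 × 210 = 420 values to Day 84 for 30 children (plus the later mucormycosis visits), and one table, one listing and an optional plot. No extra ECG, blood draw or visit is needed. Transcription and checking of the values at about 30 sites is the main burden.
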